1.5 End of Therapy (EOT)

Administration of study drug may occur on the same calendar day as the EOT visit, and if so will be completed before the EOT assessments begin. If the last dose of the study drug or treatment regimen occurs at night, the EOT assessments (with the exception of the ECG recording) can be performed in the morning of the following day.

1. Unless deemed a treatment failure, administer study drug therapy: Infusion 1 over 30 (\pm 10) minutes immediately followed by Infusion 2 over 30 (\pm 10) minutes, q12h (\pm 2 hours). If a treatment failure, complete EOT visit assessments
2. Administer CAP-Symptom 18 questionnaire prior to any other study related procedures (see [Appendix I](#)). This questionnaire should be read to the patient and the patient is to provide a response without any assistance or interpretation
3. Record any new concomitant medications
4. Perform a brief physical examination including:
 - General appearance, including skin
 - Cardiovascular system
 - Lungs
 - Abdomen
5. Evaluate and record their CABP signs and symptoms, which include, but may not be limited to, cough, pleuritic chest pain, dyspnoea and sputum production and character. Categorize the symptom intensity by using the AE variable of Absent, Mild, Moderate or Severe (see Section 6.4.3). For the purposes of this study, also record patient's ability to maintain oral intake and mental status. Categorize their

mental status as normal or altered (reference definition of mental status in [Appendix D](#))

6. Record resting vital signs including heart rate, blood pressure (measure after patient has been in a supine position for 5 minutes), respiratory rate, oxygen saturation, and temperature (oral, rectal or tympanic). Measure the patient's temperature (oral, rectal, or tympanic) in the morning and afternoon, record the highest daily temperature (oral, rectal, or tympanic)
7. Obtain one 12-lead ECG recording within 60 minutes of the end of Infusion 2
8. Laboratory tests: Do not obtain EOT laboratory tests if previous laboratory tests were within prior 24 hours. If not, obtain blood and urine samples as required by the Schedule of Assessments, see Table 1 and reference the Laboratory Manual for specific information on the collection, processing, handling, storage and shipping of samples, see Section 7.1 for blood volumes and [Appendix G](#) for identification of laboratory tests
9. Additional laboratory tests: obtain additional blood and urine samples as required by the Schedule of Assessments, see Table 1, along with any other medically indicated as determined by the Investigator. Reference the Laboratory Manual for specific information on the collection, processing, handling, storage and shipping of samples, Section 7.1 for blood volumes, and [Appendix G](#) for identification of laboratory tests
10. Estimate the patient's CL_{CR} using the serum creatinine value (in conventional units) and according to the Cockcroft-Gault formula, if applicable, see Section 5.5.3 for dose adjustment. Severely impaired renal function is defined as $CL_{CR} \leq 30$ mL/min

$$\begin{aligned} \text{Males: } CL_{CR} &= \frac{(140 - \text{age}) \times (\text{kg body weight})}{(72 \times \text{mg/dl serum creatinine})} \\ \text{Females: } CL_{CR} &= \frac{(140 - \text{age}) \times (\text{kg body weight}) \times 0.85}{(72 \times \text{mg/dl serum creatinine})} \end{aligned}$$

Where age is expressed in years, weight in kg, serum creatinine in mg/dL

11. If female, conduct a urine pregnancy test, which is sensitive to at least 50 mU/mL of β -hCG. Females of childbearing potential and those who are fewer than 2 years post-menopausal must test negative prior to randomization

12. Assess, identify, and record any AEs or SAEs (see Section 6.4), as applicable, contact AstraZeneca
13. Obtain microbiological specimens, if medically indicated:
 - If deemed a treatment failure, obtain appropriate sputum specimen and provide to the local laboratory to culture, perform Gram's stain and susceptibility testing. Sputum induction (eg, via nebulisation) should be performed by appropriately trained personnel (eg, a respiratory therapist), if medically indicated. Attempts to collect an adequate sputum sample may be repeated if appropriate. Ensure that all isolates that are not contaminants are sent to the central laboratory for confirmation of organism identity and susceptibility (see Section 6.3.1.1)
 - Obtain pleural fluid specimen only if medically indicated, repeat samples are not required. Collect fluid in one aerobic blood culture bottle and one anaerobic blood culture bottle for a total of two bottles. Provide specimen to the local laboratory to culture, perform Gram's stain and susceptibility testing. Ensure that **all** isolates are sent to the central laboratory for confirmation of organism identity and susceptibility (see Section 6.3.1.2)
 - If deemed a treatment failure, or if results from previous sample test positive (rather than daily), obtain a blood culture until sterilization is confirmed in those patients with a positive result at baseline (ie, baseline blood culture grows an organism other than those judged to be transient or resident skin flora). Obtain one aerobic and one anaerobic bottle of blood from two separate sites for a total of four bottles. Perform culture and susceptibility testing at the local laboratory and send isolates, other than those judged to be transient or resident skin flora, to the central laboratory for confirmation of organism identity and susceptibility. Susceptibility testing of all isolates sent to the central laboratory will be performed by broth microdilution tests and CLSI disk diffusion tests (see Section 6.3.1.4)

Refer to the Laboratory Manual for specific procedures pertaining to the collection, processing, storage, and shipment of all specimens / cultures.

14. Determine clinical outcome according to Section 6.3.2.

1.6 Test of Cure (TOC)

Perform TOC assessments 8 to 15 days after the last dose of the study treatment regimen is administered.

1. Administer CAP-Symptom 18 questionnaire prior to any other study related procedures (see [Appendix I](#)). This questionnaire should be read to the patient and the patient is to provide a response without any assistance or interpretation
2. Record any new concomitant medications
3. Perform a brief physical examination including:
 - General appearance, including skin
 - Cardiovascular system
 - Lungs
 - Abdomen
4. Evaluate and record their CABP signs and symptoms, which include, but may not be limited to, cough, pleuritic chest pain, dyspnoea and sputum production and character. Categorize the symptom intensity by using the AE variable of Absent, Mild, Moderate or Severe (see Section 6.4.3). For the purposes of this study, also record patient's ability to maintain oral intake and mental status. Categorize their mental status as normal or altered (reference definition of mental status in [Appendix D](#))
5. Record resting vital signs including heart rate, blood pressure (measure after patient has been in a supine position for 5 minutes), respiratory rate, oxygen saturation (if medically indicated), and temperature (oral, rectal or tympanic). Measure the patient's temperature (oral, rectal, or tympanic) in the morning and afternoon, record the highest daily temperature (oral, rectal, or tympanic)
6. Obtain one 12-lead ECG recording
7. Obtain CXR posteroanterior or chest CT scan, unless the subject was deemed a failure at the EOT visit. If the patient's condition does not allow for a standard posteroanterior, a portable anteroposterior CXR is acceptable
8. Laboratory tests: obtain blood and urine samples as required by the Schedule of Assessments, see Table 1. Reference the Laboratory Manual for specific information on the collection, processing, handling, storage and shipping of samples, Section 7.1 for blood volumes, and [Appendix G](#) for identification of laboratory tests
9. Additional laboratory tests: obtain additional blood and urine samples as required by the Schedule of Assessments, see Table 1, along with any other medically indicated as determined by the Investigator. Reference the Laboratory Manual for specific information on the collection, processing, handling, storage and shipping of

samples, Section 7.1 for blood volumes, and [Appendix G](#) for identification of laboratory tests

10. Assess, identify, and record any AEs or SAEs (see Section 6.4), as applicable, contact AstraZeneca
11. Obtain microbiological specimens,
 - If not previously categorized as a treatment failure at EOT and is now a treatment failure, obtain appropriate sputum specimen, and provide to the local laboratory to culture, perform Gram's stain and susceptibility testing. Sputum induction (eg, via nebulisation) should be performed by appropriately trained personnel (eg, a respiratory therapist), if medically indicated. Attempts to collect an adequate sputum sample may be repeated if appropriate. Ensure that all isolates that are not contaminants are sent to the central laboratory for confirmation of organism identity and susceptibility (see Section 6.3.1.1)
 - Obtain pleural fluid specimen only if medically indicated, repeat samples are not required. Collect fluid in one aerobic blood culture bottle and one anaerobic blood culture bottle for a total of two bottles. Provide specimen to the local laboratory to culture, perform Gram's stain and susceptibility testing Ensure that **all** isolates are sent to the central laboratory for confirmation of organism identity and susceptibility (see Section 6.3.1.2)
 - If not previously categorised as a treatment failure at EOT and is now a treatment failure, obtain blood cultures or repeat blood cultures upon receipt of a positive result (rather than daily) until sterilization is confirmed in those patients with a positive result at baseline (ie, baseline blood culture grows an organism other than those judged to be transient or resident skin flora). Obtain one aerobic and one anaerobic bottle of blood from two separate sites for a total of four bottles. Perform culture and susceptibility testing at the local laboratory and send isolates, other than those judged to be transient or resident skin flora, to the central laboratory for confirmation of organism identity and susceptibility. Susceptibility testing of all isolates sent to the central laboratory will be performed by broth microdilution tests and CLSI disk diffusion tests (see Section 6.3.1.4)

Refer to the Laboratory Manual for specific procedures pertaining to the collection, processing, storage, and shipment of all specimens / culture

12. If not previously categorised as a treatment failure, determine patient outcome according to Section 6.3

1.7 Late Follow-up Visit (LFU)

A LFU visit should be performed 21 to 35 days after the last dose of the study drug therapy is administered. Patients who were considered clinically cured at the TOC will be reassessed at this visit (see Section 6.3.2.2 and Table 5 for evidence of continuing response, i.e. no relapse)

1. Administer CAP-Symptom 18 questionnaire prior to any other study related procedures (see [Appendix I](#)). This questionnaire should be read to the patient and the patient is to provide a response without any assistance or interpretation
2. Record any new concomitant medications.
3. Evaluate and record their CABP signs and symptoms, which include, but may not be limited to, cough, pleuritic chest pain, dyspnoea and sputum production and character. Categorize the symptom intensity by using the AE variable of Absent, Mild, Moderate or Severe (see Section 6.4.3). For the purposes of this study, also record patient's ability to maintain oral intake and mental status. Categorize their mental status as normal or altered (reference definition of mental status in [Appendix D](#))
4. Obtain CXR (posteroanterior) or chest CT scan, unless the patient was deemed a failure at the EOT or TOC visit. If the patient's condition does not allow for a standard posteroanterior examination, a portable anteroposterior CXR is acceptable
5. Additional laboratory tests: obtain additional blood and urine samples as required by the Schedule of Assessments, see Table 1, along with any other medically indicated as determined by the Investigator. Refer to Section 7.1 for blood volumes, [Appendix G](#) for identification of laboratory tests and the Laboratory Manual for specific information on the collection, processing, handling, storage and shipping of samples
6. In patients experiencing clinical relapse, a microbiological examination will be performed if clinically appropriate. Obtain microbiological specimens, if medically indicated
 - Obtain appropriate sputum specimen and provide to the local laboratory to culture, perform Gram's stain and susceptibility testing. Sputum induction (eg, via nebulisation) should be performed by appropriately trained personnel (eg, a respiratory therapist), if medically indicated. Attempts to collect an adequate sputum sample may be repeated if appropriate. Ensure that all isolates that are not contaminants are sent to the central laboratory for confirmation of organism identity and susceptibility (see Section 6.3.1.1)
 - Obtain pleural fluid specimen only if medically indicated, repeat samples are not required. Collect fluid in one aerobic blood culture bottle and one

anaerobic blood culture bottle for a total of two bottles. Provide specimen to the local laboratory to culture, perform Gram's stain and susceptibility testing. Ensure that **all** isolates are sent to the central laboratory for confirmation of organism identity and susceptibility (see Section 6.3.1.2)

- Repeat blood cultures upon receipt of a positive result (rather than daily) until sterilization is confirmed in those patients with a positive result at baseline (ie, baseline blood culture grows an organism other than those judged to be transient or resident skin flora). Obtain one aerobic and one anaerobic bottle of blood from two separate sites for a total of four bottles. Perform culture and susceptibility testing at the local laboratory and send isolates, other than those judged to be transient or resident skin flora, to the central laboratory for confirmation of organism identity and susceptibility. Susceptibility testing of all isolates sent to the central laboratory will be performed by broth microdilution tests and CLSI disk diffusion tests (see Section 6.3.1.4)

Refer to the Laboratory Manual for specific procedures pertaining to the collection, processing, storage, and shipment of all specimens / culture

7. Assess, identify, and record SAEs (see Section 6.4), as applicable, contact AstraZeneca.
8. Capture 'Resource Use' information

Clinical Study Protocol Appendix I

Drug Substance	Ceftaroline fosamil
Study Code	D3720C00002
Edition Number	1.0

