6.3 Efficacy

6.3.1 Microbiological Assessments of CABP

6.3.1.1 Sputum Samples for Culture

Obtain adequate sputum samples for culture, Gram's staining, and susceptibility testing at baseline, during the study drug period (Study Day 1 up to Day 7) if medically indicated; at the EOT and TOC visits, if the patient is deemed a clinical failure or if medically indicated; and at the LFU visit if medically indicated and the patient is relapsing. Sputum samples are not obtained at the TOC or LFU visits if the patient was previously deemed a failure. Sputum induction (eg, via nebulisation) should be performed by appropriately trained personnel (eg, a respiratory therapist), if medically indicated. Attempts to collect an adequate sputum sample may be repeated if appropriate. Perform culture and susceptibility testing at the local laboratory and send all isolates that are not contaminants (see list below) to the central laboratory for confirmation of organism identity and susceptibility.

The following organisms are considered sputum contaminants, rather than primary pathogens of CABP, and should not be sent to the central laboratory for confirmation of organism identity and susceptibility:

- Fungi (yeast and molds, eg, *Candida spp.* and *Aspergillus spp.*), unless there is evidence of a secondary fungal infection
- *Enterococcus spp.* or Group D *streptococci*
- *Viridans streptococci*
- *Coagulase-negative staphylococci*
- *Micrococcus spp.*
- *Neisseria spp.* other than *N. meningitidis* and *N. gonorrhoeae*
- *Corynebacterium spp.* and other coryneforms
- *Lactobacillus spp.*
- *Vibrio spp.*
- *Capnocytophaga spp.*
- *Cardiobacterium spp.*
- *Flavobacterium spp.*

Susceptibility testing of all isolates sent to the central laboratory will be performed by broth microdilution tests (to determine the MIC) and Clinical Laboratory Standards Institute (CLSI)

disk diffusion tests. Refer to the Laboratory Manual for specific procedures pertaining to the collection, processing, storage, and shipment of sputum cultures.

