6.3.1.3 Blood Samples for Culture

Obtain blood for culture at baseline and as medically indicated from Study Day 1 to the TOC visit. Repeat blood cultures upon receipt of a positive result (rather than daily) until sterilization is confirmed in those patients with a positive result at baseline (ie, baseline blood culture grows an organism other than those judged to be transient or resident skin flora). Obtain blood for culture at the LFU visit only if medically indicated and the patient is experiencing clinical relapse. Blood for culture is not obtained at the TOC or LFU visits if the patient was previously deemed a failure.

When blood cultures are required, obtain one aerobic bottle and one anaerobic bottle from two separate sites for a total of four bottles. Perform culture and susceptibility testing at the local laboratory and send isolates, other than those judged to be transient or resident skin flora, to the central laboratory for confirmation of organism identity and susceptibility. Susceptibility testing of all isolates sent to the central laboratory will be performed by broth microdilution tests and CLSI disk diffusion tests.

Refer to the Laboratory Manual for specific procedures pertaining to the collection, processing, storage, and shipment of blood cultures.

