6.3.4 Microbiological Response Definitions

6.3.4.1 Per-Pathogen Microbiological Response

A microbiological outcome at the TOC visit will be determined in the mMITT and ME populations for each pathogen isolated at baseline (see

[Table 7](#)). Microbiological outcome categories are eradication, presumed eradication, persistence, presumed persistence, and indeterminate, as defined in the table below. Favourable microbiological outcomes are eradication or presumed eradication. Unfavourable microbiological outcomes are persistence or presumed persistence.

Table 7 Microbiological Outcome Categories

Outcome ^a	Definition	
Favourable	Eradication	An adequate source specimen ^b demonstrates absence of the original baseline pathogen.
	Presumed eradication	An adequate source specimen ^b was not available to culture and the patient was assessed as a clinical cure.
Unfavourable	Persistence	Source specimen demonstrates continued presence of the original baseline pathogen.
	Presumed persistence	An adequate source specimen ^b was not available to culture and the patient was assessed as a clinical failure.
Indeterminate	Indeterminate	An adequate source specimen ^b was not available to culture and the patient's clinical response was assessed as indeterminate.

^a The microbiological outcomes at TOC are only applicable to patients who are not clinical failures at EOT. Patients who are failures at EOT will have the corresponding microbiological outcome determined from EOT cultures and carried forward to TOC. If no EOT culture is available for patients who are clinical failures at EOT, then the microbiological outcome at TOC will be presumed persistence. Otherwise, the microbiological outcome at TOC will be determined from cultures obtained at the TOC visit window. If no culture is available in the TOC window then the microbiological outcome at TOC will be presumed from the clinical response (see [Table 5](#)) at TOC.

^b An adequate source specimen is defined as any sample that may yield the growth of a CABP pathogen eg, blood, respiratory specimens, or pleural fluid.

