6.3.4.3 Microbiological Categories for Pathogens Identified After Baseline Assessment

Microbiological categories for pathogens identified after the baseline assessment are super-infection, new infection, colonization, and re-infection or recurrence, as defined in [Table 8](#).

Table 8 Categorization of Bacterial Pathogens Identified After Baseline Assessment

Super-infection	Isolation of a new pathogen(s) (other than the original baseline pathogen(s)) during the period up to and including EOT from cultures of the original CABP, or a new CABP at the same site, regardless of susceptibility to study drugs, in a patient who has signs and symptoms of infection requiring alternative antimicrobial therapy.
New Infection	Isolation of a new pathogen (other than the original baseline pathogen) determined at TOC or LFU regardless of susceptibility to study drugs, in a patient who has signs and symptoms of infection requiring alternative antimicrobial therapy
Colonization	Isolation of an organism from the original CABP site that is not associated with signs and symptoms of active infection and does not require antimicrobial therapy. Colonization will be determined only at EOT and TOC when an assessment of clinical response is performed.
Microbiologic re-infection or recurrence	Isolation of a baseline pathogen from the original CABP site, at the LFU visit, in patients who had favourable clinical and microbiological responses at TOC. To be defined as a recurrent infection, pathogens must be associated with emergence or worsening of clinical signs and symptoms, with or without laboratory evidence of active infection, and require antimicrobial therapy.

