Per-Patient Microbiological Re-infection/Recurrence Rate at the LFU Visit

This analysis will be performed in the subset of patients in the ME Population who had a favourable microbiological outcome at the TOC visit. The number and percentage of patients in each treatment group that have a re-infection or recurrence at the LFU visit will be tabulated.

Two-sided 95% CI for the difference in re-infection/recurrence rates (ceftaroline minus ceftriaxone) will be constructed using the method proposed for stratified designs by Miettinen and Nurminen (Miettinen O et al 1985). Cochran-Mantel-Haenzel weights will be used for the stratum weights (defined by district) in the calculation of the CI.

Table 10 Secondary Efficacy Endpoints

Population	Subset(s)	Assessment	Per-patient Evaluation	Outcomes
MITT, mMITT and ME		TOC	Clinical response	Cure Failure Indeterminate (MITT and mMITT)
MITT and CE		EOT	Clinical response	Cure Failure Indeterminate (MITT only)
mMITT and ME		TOC	Microbiological response	Favourable: eradication or presumed eradication Unfavourable: persistence, presumed persistence, or indeterminate (mMITT only)

Population	Subset(s)	Assessment	Per-patient Evaluation	Outcomes
MITT and CE		TOC	Overall response	Success: clinical cure and either a radiographic success or radiographic indeterminate Failure: either clinical failure or clinical indeterminate, or radiographic failure
mMITT and ME	Per pathogen	TOC	Clinical response	Cure Failure Indeterminate (mMITT only)
mMITT and ME	Per pathogen	TOC	Microbiological response	Favourable: eradication or presumed eradication Unfavourable: persistence, presumed persistence, or indeterminate (mMITT only)
CE	Clinically cured at TOC	LFU	Clinical response	Continued response Relapse
ME	Micro-biologically favourable outcome at TOC	LFU	Microbiological re-infection / recurrence	No re-infection or recurrence Re-infection or recurrence

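### A relapsing patient with no culture at late follow-up is scored by default as having no microbiological recurrence, so this secondary rate is understated

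*Protocol*

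**What the plan says.** **Event.** Table 8 (section 6.3.4.3) defines re-infection or recurrence as "Isolation of a baseline pathogen from the original CABP site, at the LFU visit", together with new or worse signs and symptoms that need antimicrobial therapy. It has no presumed category.

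**Analysis set and levels.** Section 12.2.2.2 analyses all ME patients whose microbiological outcome at TOC was favourable. It does not require an LFU specimen. Table 10 lists the outcomes as "No re-infection or recurrence Re-infection or recurrence", that is, two levels and nothing else.

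**Sampling at LFU.**
- Appendix H, 1.7, step 6: "In patients experiencing clinical relapse, a microbiological examination will be performed if clinically appropriate". Its blood-culture bullet describes repeat cultures "until sterilization is confirmed in those patients with a positive result at baseline".
- Section 6.3.1.1, sputum: "at the LFU visit if medically indicated and the patient is relapsing".
- Section 6.3.1.3, blood: "Obtain blood for culture at the LFU visit only if medically indicated and the patient is experiencing clinical relapse".
- Table 1, footnotes w (sputum) and y (blood): culture at LFU if medically indicated, with relapse given as an example of an indication.

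**TOC, for contrast.** Table 7 (section 6.3.4.1) scores presumed persistence, an unfavourable outcome, when an adequate specimen "was not available to culture and the patient was assessed as a clinical failure".

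**The concern.** Relapse under section 6.3.2.2 means returning signs and symptoms that require more antimicrobial therapy. Such a patient already meets the clinical part of the Table 8 definition. Only the isolate can be lacking, and it may be lacking because no specimen was taken. With two levels and a denominator that does not depend on culture, a missing specimen in a patient who is doing badly becomes a good microbiological result. At TOC the protocol does the reverse: a clinical failure without a specimen is never scored as favourable.

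At stake is one named secondary endpoint. Its rate would be too low in both arms, it would depend partly on how readily sites culture relapsing patients, and its no-recurrence group could include patients who relapsed and needed new antibiotics.

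**Working it through.** **1. The protocol's own figure.** Section 12.3 uses 85% cure in both arms, a 10% margin, 90% power and 77.5% evaluability. With a one-sided 0.025 level:

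n per arm = (1.960 + 1.282)² × 2 × 0.85 × 0.15 / 0.10² = 268 evaluable; 268 / 0.775 = 346; total 692.

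This reproduces the stated 692. It plays no part in the scoring problem and is used below only to size the ME group. The protocol states no figure for the LFU recurrence endpoint.

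**2. The scoring, for a relapsing ME patient who was favourable at TOC.**

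| LFU specimen | In denominator? | Can be counted as recurrence? | Level left in Table 10 |
|---|---|---|---|
| Baseline pathogen isolated | Yes | Yes | Recurrence |
| Adequate specimen, pathogen absent | Yes | No | No recurrence |
| No adequate specimen | Yes | No | No recurrence |

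The last two rows get the same score although only the second rests on evidence. Two rules elsewhere do not close the gap. Presuming the outcome from clinical response (Table 7) is limited to TOC. The indeterminate class for unavailable LFU data (section 6.3.2.2) is stated for clinical relapse only.

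**3. Size.** Let p be the true recurrence rate and c the share of true recurrences that are cultured. If culture yield is complete, the reported rate is p × c. If c is the same in both arms, the arm difference shrinks by the same factor. Neither p nor c is in the protocol, so both are assumed:

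| True rate p | c = 75% | c = 50% | c = 25% |
|---|---|---|---|
| 2% | 1.5% | 1.0% | 0.5% |
| 4% | 3.0% | 2.0% | 1.0% |
| 5% | 3.75% | 2.5% | 1.25% |

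If c differed by arm, say 80% against 50%, equal true rates would show a spurious difference of p × 0.30, which is 0.6 points at 2% and 1.5 points at 5%.

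**4. Numbers at risk.** Planned Clinically Evaluable (CE) patients: 692 × 0.775 = 536. Assuming ME is 20% to 40% of CE and 85% are favourable at TOC: 536 × 0.20 × 0.85 = 91, and 536 × 0.40 × 0.85 = 182. At true rates of 2% to 5% this gives 91 × 0.02 = 1.8 to 182 × 0.05 = 9.1 true recurrences over both arms. With about 45 to 91 patients per arm, each uncultured relapser leaves that arm's rate uncertain by 1/91 = 1.1 to 1/45 = 2.2 points.

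**5. Against sampling error.** At 4% in both arms, a simple 95% interval for the difference has half-width 1.96 × √(2 × 0.04 × 0.96 / n). That is about 6 points for n = 91 and 8 points for n = 45. The scoring effect is large relative to the rate but small next to the uncertainty in the difference.

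**The case against.** **The default is inferred.** No sentence says that an uncultured relapser counts as free of recurrence. Table 10 is also not a complete list of levels: its clinical relapse row omits the indeterminate class that section 6.3.2.2 assigns, and a SAP could add one here. This is fair as to certainty. Still, the numerator, denominator and levels are all fixed in the protocol, and together they leave no other place for the patient.

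**Culture in relapse is the expected course.** Footnotes w and y of Table 1 name relapse as an example of a medical indication, and footnote y and section 6.3.1.3 are not confined to patients with a positive baseline blood culture. This stands, and it limits the likely size. It does not remove the discretion in sections 6.3.1.1 and 6.3.1.3 or in Appendix H, 1.7.

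**The contrast with TOC is not clean on collection.** Appendix H, 1.6 reads "If not previously categorized as a treatment failure at EOT and is now a treatment failure, obtain appropriate sputum specimen", but section 12.1.1.5 takes TOC specimens only when medically indicated and expects many patients to have none. This stands too. The contrast should therefore rest on scoring (Table 7), not on collection.

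**The patients are not lost.** ME is a subset of CE, and section 12.2.2.2 counts relapse in CE patients cured at TOC. These relapses appear there. Only the microbiological rate is understated.

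**Requiring an isolate is a legitimate definition.** A relapse may be due to another organism, for which Table 8 has a new-infection category. A reader might infer that every uncultured relapser should be scored as a presumed recurrence. The documents do not support that: it would attribute the relapse to the baseline pathogen without evidence.

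**Conclusion.** The point holds as a scoring gap. As written, a relapsing patient without an adequate LFU specimen is placed by default with the patients free of recurrence, and the microbiological recurrence rate is understated. The proportional form (half cultured, half reported) assumes complete culture yield and, for the arm difference, equal culturing in both arms. The recurrence rate, the share cultured and the ME fraction are all assumptions. In absolute terms the effect is probably small.

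A reader might go further and infer a biased treatment comparison or damage to the trial's conclusion. The documents do not support this. The endpoint is secondary, has few expected events and carries no decision rule, only a tabulation and a confidence interval. The trial is double-blind and randomisation is stratified by district, so culturing habits should be broadly balanced between arms. The primary analysis, the sample size and the clinical relapse endpoint are untouched.

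**What to change.** 1. In Tables 8 and 10, add a third level for this endpoint: *indeterminate: clinical relapse without an adequate LFU specimen*. State that it is never classed as free of recurrence.
2. In section 12.2.2.2, keep these patients in the analysis set and show them on their own line. Dropping them from the denominator would introduce a bias of its own. Report per arm the number of relapsers and the number of those cultured.
3. Give the recurrence rate and its confidence interval twice on the same denominator, once with indeterminates counted as recurrence and once with them not counted. The two results bound the effect of the missing specimens without guessing the organism.
4. Reconcile the LFU culture wording in Table 1 footnotes w and y, sections 6.3.1.1 and 6.3.1.3, and Appendix H, 1.7, step 6, including its blood-culture bullet. Which patients are to be cultured is a clinical decision for the sponsor and is not proposed here.

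The cost is one more category and one sensitivity analysis. The reported recurrence rate may be slightly higher. Items 1 to 3 require no additional specimens.
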